6.1 Randomization

The study will be double-blinded (blinded for the study subjects as well as for the investigator). Throughout the trial the blind must not be broken, only in case of emergency, in which case sealed emergency envelopes containing the name of the enrichment material will be available. The consumption of experimental product must be discontinued if the code has been broken for any reason. Every code breaking has to be reported to the WP5 leader.

A total number of 300 participants will be enrolled into the study. The complete sample size will be equally distributed between three centres responsible for either bakery, dairy or egg products, which results in a sample size of 100 per centre. In each centre participants will be divided in 5 groups of 20 each receiving BEF formulated using a specific matrix (bakery, dairy or egg-based), and enriched with DHA, BG, or AC alone or DHA+BG, or DHA+AC. The allocation of participants to the different groups will be carried out based on predefined randomization lists created separately for each pilot study. All three randomization lists will be prepared with a sample size of 120, with a block size of 5 and with an allocation ratio of 1:1:1:1:1. In case of withdrawn of a volunteer, he/she will be substituted by a new one. For this purpose, an additional sample size of 20 will be applied for each pilot study. Gender will be considered as a stratum with a ratio near to 1:1. Each randomization list will consist of a three-digit randomization number from 101 to 160 for male and from 201 to 260 for female participants with the name and code of the assigned enrichment material. The prepared randomization lists will be sent to the manufacturers of each product, who will pack and label the products according the list and send them to the centres.

A three-digit unique randomization number will be assigned to each individual recruited volunteer, which will determine the allocation of the products. Randomization numbers will be distributed in ascending order with the starting number of 101 in each centre. Centres will also get a unique one-digit centre identifier. Therefore volunteers will be identified by a centre and a participant codes.

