9.17 Food preferences questionnaire

Food preferences questionnaire

Randomisation ID

Screening ID

Please read the following questions and place an X in the appropriate box.

1. In general, would you say your health is:

- Very bad
- Bad
- Moderate
- Good
- Excellent

2. How often do you eat these types of products?

	Every day	Every week	Every two weeks	Once a month	Less than once a month	Never
Biscuits						
Milkshake						
Pancake						

3. What do you think about the **appearance** of the pancakes?

1	2	3	4	5	6	7	8	9
I dislike extremely								I like extremely

Comments: positive:

negative:

4. How would you rate the **overall aroma / odour** of the pancakes?

1	2	3	4	5	6	7	8	9
I dislike extremely								I like extremely

Comments: positive:

negative:

5. How would you rate the **overall taste** of the sample?

1	2	3	4	5	6	7	8	9
I dislike extremely								I like extremely

Comments: positive:

negative:

6. What do you think about the **texture** of the pancakes?

1	2	3	4	5	6	7	8	9
I dislike extremely								I like extremely

Comments: positive:

negative:

7. How much do you like the pancakes **overall**?

1	2	3	4	5	6	7	8	9
----------	----------	----------	----------	----------	----------	----------	----------	----------

I dislike extremely								I like extremely
--------------------------------	--	--	--	--	--	--	--	-----------------------------

Comments: positive:

negative:

8. How much do you like the pancakes **overall** if they contribute to improving your health?

1	2	3	4	5	6	7	8	9
I dislike extremely								I like extremely

Comments: positive:

negative:

Thank you for your help!

9.18 24 hour dietary recall

24 hour dietary recall

Randomisation ID

Screening ID

We would like you to record all the food and drinks you have consumed during the last 24 hours. Begin with the most recent, this could be today, and work back to the same time yesterday.

Please answer the following questions:

1. Enter today's date.

/ /

Day Month Year

2. Which day(s) of the week does this record?

Sun Mon Tue Wed Thu Fri Sat

3. Is this a typical day?

Yes No

If not, give an example of a typical day after yesterday's record, if you wish.

Continue to page 2

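### The protocol discloses a fixed block of five for five arms, so any allocation that becomes known narrows the rest of its block; the numbering sentence also needs a start for women

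*Protocol*

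**What the plan says.** Protocol section 6.1 fixes the randomisation in some detail. Each centre has its own list of 120 numbers, drawn up "with a block size of 5 and with an allocation ratio of 1:1:1:1:1". Sex is a stratification factor: "Gender will be considered as a stratum with a ratio near to 1:1". The numbers run "from 101 to 160 for male and from 201 to 260 for female participants". Withdrawn volunteers are replaced: "For this purpose, an additional sample size of 20 will be applied for each pilot study".

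The following paragraph tells centres how to issue the numbers: "Randomization numbers will be distributed in ascending order with the starting number of 101 in each centre". It states no starting number for women.

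The same section declares the trial double-blind for subjects and investigator. The lists go to the manufacturers, who pack and label. Sealed envelopes naming the enrichment material are available for emergencies, and every code break must be reported to the work package leader.

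Sections 5.3 and 5.8 and annex 9.17 add that participants rate the appearance, smell, taste and texture of their product on days 1 and 28, with space for comments, and that food packages are collected on day 28.

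**The concern.** With five arms at equal ratio, 5 is the smallest possible block and the most informative one to know. Once some members of a block are known, the rest are drawn from a short list of remaining arms, and the last member is certain when the other four are known. Because section 6.1 states the block size, recruiting staff do not have to work it out.

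The products are foods that are seen, smelled and tasted, and the protocol does not state that the five BEFs within a matrix are matched on these properties. Codes can also be opened in an emergency. Annex 9.7 adds that a volunteer with an unexpectedly high final glucose is alerted after the code is broken, but it does not make clear whether the allocation code or the identity code is meant. Under section 6.2.2 the clinical researchers enrol and exclude participants, so someone who learned of earlier allocations could also influence who enters next. At stake is the comparability of arms of 20 that are to be ranked against one another.

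The numbering sentence is a smaller matter. A single start of 101 does not fit a scheme in which women's numbers begin at 201.

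**Working it through.** **Inputs, all from section 6.1:** five arms at 1:1:1:1:1; fixed block of 5; men 101–160, women 201–260; list of 120 per centre; 100 participants plus 20 in reserve.

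**The plan's own figure.** (160 − 101 + 1) + (260 − 201 + 1) = 60 + 60 = 120 = 100 + 20. Each sex list holds 60 / 5 = 12 complete blocks. With 50 men and 50 women, 10 complete blocks per sex give 10 men and 10 women per arm. The list is internally consistent.

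**Ceiling on guessing, every earlier allocation in the block known.** At place k of a block of 5, 6 − k arms remain and the best guess is right with probability 1/(6 − k):

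(1/5 + 1/4 + 1/3 + 1/2 + 1) / 5 = 2.283 / 5 = 45.7%, against 20% by chance.

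The fifth place is then certain: 100 / 5 = 20 of a centre's 100 participants.

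**Same ceiling with larger blocks.** Let r be the numbers of each arm left and t their total. Expected correct guesses are g(r) = max(r)/t + Σ (rᵢ/t) · g(r with one fewer of arm i). For a block of 10 (two of each arm) this gives 4.071 / 10 = 40.7%.

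**Mixed blocks of 5 and 10.** Someone who does not know the block boundaries cannot guess better than someone who does. As an illustration, take four blocks of 5 and four of 10 (20 + 40 = 60). The ceiling is at most (4 × 2.283 + 4 × 4.071) / 60 = 25.42 / 60 = 42.4%. Without knowledge of the boundaries the fifth place is also no longer certain.

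**Partial recognition.** Assumption, not in the documents: only the two anthocyanin-containing arms can be told from the other three. An assignment is certain as to class once the other class is used up. With a places of one class and b of the other, the expected number of such places is b/(a + 1) + a/(b + 1).

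| Block | a, b | Expected certain places | Share | Class guessed correctly |
|---|---|---|---|---|
| 5 | 2, 3 | 3/3 + 2/4 = 1.50 | 30% | 72% |
| 10 | 4, 6 | 6/5 + 4/7 = 1.77 | 17.7% | 68% |

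With no information, always naming the larger class is right 60% of the time.

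**A single emergency opening** reveals one allocation. For the remaining places in that block, at most four, the chance of a correct guess rises from 1/5 to 1/4.

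**No recognition and no code break.** The rate stays at 20% for any block size.

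**Numbering sentence read literally,** as one run from 101 regardless of sex. Participants 1–60 would take 101–160 and the remaining 40 would take 201–240. Arm sizes would stay at 20. With 50 women among 100, the number of women in an arm would have SD √(20 × 0.5 × 0.5 × 80/99) = 2.0. A simulation of 20,000 trials gives a 95% range of 6 to 14 women per arm and a mean gap of 5.2 between the highest and lowest arm. With sex-specific issue of 50 and 50 the gap is 0.

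**The case against.** The strongest reply is that a working double blind makes the block size irrelevant, and section 6.1 declares one. Nothing in the document shows that the five BEFs can be told apart. Silence about matching proves little: formulations are set in other work packages, and section 5.6 lists a composition annex that is not among the annexes in the text. Each participant receives one product and compares it with nothing. The annex 9.17 forms collect liking scores, and their use by staff to decode arms would be an inference. Day-28 comments will often come after the next enrolments in the block. Entry also depends on measured waist, blood pressure and laboratory values, which limits selective enrolment. All of this stands, and it makes the 46% a ceiling and not an expectation.

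It is also fair to say that larger blocks help only modestly under full unmasking (45.7% to 40.7%). The gain is clearer for partial recognition, where certain assignments fall from 30% to 17.7%.

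On numbering, a reader might infer that women would be given men's numbers and that stratification by sex fails. The text does not support this. The explicit male and female ranges stand in the preceding paragraph, a woman could not be given 101 without breaking them, and a single run would meet a gap after 160. Ascending order within each range is the natural reading.

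**Conclusion.** This is a minor, conditional weakness. Section 6.1 pairs the smallest possible fixed block with disclosure of its size, so information about one allocation carries over to others in its block. The size runs from nothing, if the blind holds, to at most 46% correct guesses against 20% by chance, if every earlier allocation in a block is known. The intermediate figures rest on the assumption that two of the five arms are recognisable, which the document neither states nor rules out.

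A reader might go further and conclude that allocation concealment has failed or that selective enrolment will occur. The protocol does not support that: it shows neither distinguishable products nor known allocations. What it supports is that a cheap precaution has been left out in a trial where foods are seen and tasted and codes can be opened.

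The numbering sentence is a wording conflict with the female range. It is not a failure of stratification.

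**What to change.** 1. Generate each sex list of 60 with randomly varying blocks of 5 and 10. Both sizes keep 1:1:1:1:1, and their combinations can fill 60 exactly.
2. Remove the block size from section 6.1. Record it in a document held by whoever prepares the lists, outside the protocol that centres hold.
3. Reword the numbering sentence in section 6.1: *in ascending order within each sex list, starting at 101 for men and 201 for women*.

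**Cost.** One edited passage, and lists regenerated before the manufacturers pack and label. If enrolment in a sex list stops inside a block of 10, arms can differ by at most 2 in that list, against at most 1 with blocks of 5. Over both sex lists of a centre that is at most 4 against 2. The third change costs nothing and can be made alone.

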6.2 Data Management

6.2.1 Summary

Data management consists of tasks required to capture all study data into electronic form. Data management also includes tasks designed to validate the entered data by means of a variety of edit checks (e.g., subjecting the data to range checks, valid value checks, crosschecks, and manual review) that provide feedback to those entering/providing the data. The data management guidelines are incorporated into the Data Management Plan and Data Validation Plan. Both plans will be prepared together with the electronic data capture system and will be finalized before starting to enter data into the database system.

The goal is to have an electronic clinical database that accurately reflects the data collected and is able to be used for purposes of analyzing study data for regulatory submissions and professional publication. The data capturing process and the electronic system that captures clinical data for purposes of analysis and reporting will adhere to GCP guidelines for data management systems.

6.2.2 Electronic Data Capture (EDC) System

The proposed EDC system for use in this study is Mythos CDMS v2.0. The system is validated according to GCP and 21 CFR Part 11 regulations to ensure accuracy, reliability, consistent

intended performance, and the ability to discern invalid or altered records. The EDC system is hosted by AdWare Research Ltd.

Mythos is a web application based on Oracle 10gR2 database and accessible through secure Internet connection via a common modern web browser. Statistical analysis is performed with SAS 9.2. Data transfer tool used to access data from statistical analysis software is SAS Oracle Data Transfer. Database and daily backups are stored on mirrored hard drives at a secured location with access control. Disaster Recovery Plan, uninterruptible power supply and comprehensive malware protection are also provided.

Site staff will be trained on CRF best practices and system use. Users are authorized by their electronic signature. All study participants are provided different levels of access based on the participant's role:

- Level 1 access (clinical researcher): enrol/exclude patients, complete/modify eCRFs, answer queries, upload in the system data of patient enrolled by him/her, can access patient data enrolled by him/her.
- Level 2 access (study monitor): verify/approve eCRFs, raise/close queries, can view all data, but can't modify them.
- Level 3 access (coordinator and WP5 leader): can view all patients data, but cannot modify them.
- Level 4 access (principal investigator - one in each centre): same as clinical researcher. In addition he/she can access all data and can modify them if needed. All modification must be recorded, and coordinator and WP5 leader must be informed before data modification.
- Level 5 access (administrator): can't view any patient data; can upload files of shared documents (eg. protocol outline, printable informed consent form and adverse event/serious adverse event forms, etc.), can manage sites, user accounts, can open/close study or parts of the study.

Audit trail of all database transactions – including names and dates corresponding to each entry-of or change-to a field – is managed automatically by the EDC system.

The data entry into EDC system is performed by investigators from source documents. The EDC system provides real-time data quality control (like range- and validity checks, etc.). Site monitor access to clinical data is facilitated to enable source document verification. Data managers provide status reports for enrolment, CRF completion, outstanding queries, query overrides, perform medical coding of adverse events and concomitant medications, conduct SAE and AE database reconciliation, perform data cleaning, query generation, query resolution, update database based on query responses, perform audit of final database, lock database and archive database files, completed CRFs, and query records. Disaster Recovery Plan will be provided as an annex of the Data Management Plan.

Data management processes and activities are controlled by the standard operating procedures of AdWare Research Ltd.

6.3 *Statistical Evaluation*

6.3.1 Analysis Datasets

- The full analysis dataset (FAS) is defined as all randomized subjects who received at least one dose of experimental product and have primary outcome data both at baseline and at the end of the study.

- The safety analysis dataset (SD) is defined as all randomized subjects who received at least one dose of experimental product.

A total number of 300 participants will be enrolled into the study. The complete sample size will be equally distributed between three centres responsible for either bakery, dairy or egg products, which results in a sample size of 100 per centre. In each centre participants will be divided in 5 groups of 20 each receiving BEF from a specific matrix, and enriched with DHA, BG, or AC alone or DHA+BG, or DHA+AC. The allocation of patients to the different groups will be carried out based on predefined randomization lists created separately for each pilot study.

6.4 *Statistical Analysis*

The primary and secondary analyses will be performed on the FAS dataset. Descriptive statistics for both of the primary and secondary variables will also be provided on the SD dataset. The evaluation will be done using the SAS 9.2 (or later) program package version.

Mean change in blood TG and HDL-cholesterol (primary endpoints) will be analyzed with a mixed linear model including food matrix and type of enrichment as fixed effects. If the model indicates significant differences among groups, post-hoc tests will be applied for pair wise comparisons.

Secondary endpoint variables will be analyzed similarly. Descriptive statistics for both of the primary and secondary parameters will be provided including the mean, median, minimum, maximum, standard deviation, standard error of the mean and number of cases. Mean changes (and their 95% CI) from baseline to end-of-study visit will be presented.

For safety data, descriptive statistics and individual listings of eventual adverse events (adverse events linked to venous punctures, digestive troubles following BEF ingestion, symptoms of allergy or any unexpected health event) will be also presented.

7. **Ethics**

Prior to initiating the pilot study, ethical approval will be obtained from the relevant local research ethics committees of the participating countries. Each recruitment centre will be responsible for obtaining ethical approval from their respective ethical committee. Adverts for recruitment, screening questionnaires and letters for doctors will be harmonised, but each centre may use their participant information sheets and consent forms when the local ethical committee requires that.

Before submission to the local Ethic Committee, the PATHWAY-27 Ethical Advisory Board will approve all documents. All protocols for experiments with human subjects will require approval by the members of PATHWAY-27 Ethical Advisory Board before experiments can start, and this process will take place prior to submission of those protocols to the relevant local research ethics bodies. In case of disagreement, the PATHWAY-27 Ethical Advisory Board will make the final decision as to the ethical suitability or otherwise of the studies proposed. No experiments involving human subjects will proceed without approval of the PATHWAY-27 Ethical Advisory Board and the relevant local ethics committee. Copies of approval from the REC (Research Ethics Committee) will be provided to the European Commission prior to commencing the research.

During the research period, any change of protocol must be reported to the PATHWAY-27 Ethical Committee and local ethics committees.

8. Study registration

This multi-centre study will be registered in clinicaltrials.gov.

9. Annexes

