5.3 Outcome assessment

Primary outcome: fasting serum TG and HDL-cholesterol will be measured at baseline and at the end of the study by standardized enzymatic methods.

Secondary outcomes (days 1 and 28):

- blood pressure
- body height and weight, BMI
- abdominal circumference
- blood glucose

At the beginning of the study participants will be asked to complete a food frequency questionnaire specific to the foods described on the restriction list. The purpose of this is to collect information about exposure to the bioactive ingredients from natural sources and highlight high/low level consumption that could be a potential confounding factor.

Participants at Leeds will also complete a 24 hour dietary recall at the baseline and end visit to collect information about energy, nutrient and alcohol intake. The purpose of this exercise is two-fold. Firstly to look for potential confounding factors, and secondly to investigate whether this type of dietary assessment tool is appropriate to capture the information required to perform an effective dietary assessment.

At the baseline and final visit participants will provide information about abdominal symptoms that they experience. This has been designed to assess whether the BEF have an impact on appetite and intestinal behaviour.

Participant acceptability of the BEF will be assessed at days 1 and 28 of the intervention using a food preferences questionnaire to collect data.

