Each instrument will have specific performance ranges, but generally the percentage coefficient of variation (%CV) should be below 4%. Replicate analyses will be performed for each sample.

Expected values

Normal fasting < 150 mg/dL (<1.70 mmol/L)

Normal non-fasting: < 250 mg/dL (< 2.83 mmol/L)

Borderline high: 250–500 mg/dL (2.83–5.65 mmol/L)

Hypertriglyceridemia: > 500 mg/dL (> 5.65 mmol/L)

High risk for pancreatitis: > 1000 mg/dL (> 11.30 mmol/L)

Triglyceride levels > 1000 mg/dL will be notified to the participant medical doctor.

Recording of results

Results will be collected by the clinical researcher and entered into the database for statistical analyses. Any abnormal results should be reported to the principal investigator.

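### The primary model in section 6.4 analyses change in TG and HDL-C without naming the participant's own baseline or sex; this costs precision, not validity

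*Protocol*

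**What the plan says.** Protocol section 6.4 fixes the response and the model class: "Mean change in blood TG and HDL-cholesterol (primary endpoints) will be analyzed with a mixed linear model". The terms it names are those of a "mixed linear model including food matrix and type of enrichment as fixed effects". Secondary variables are to be handled in the same way. Neither the baseline value nor sex is listed, and no scale for TG (raw, log or percent) is given.

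Both unlisted variables are available for every analysed participant:

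- **Baseline.** Under section 5.3, "fasting serum TG and HDL-cholesterol will be measured at baseline and at the end of the study". The full analysis set (6.3.1) admits only participants who "have primary outcome data both at baseline and at the end of the study", so a baseline covariate would have no missing values.
- **Sex.** Section 6.1 says "Gender will be considered as a stratum with a ratio near to 1:1". The randomisation numbers run "from 101 to 160 for male and from 201 to 260 for female participants", "with a block size of 5 and with an allocation ratio of 1:1:1:1:1".

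Entry is selected on the outcomes themselves: section 3.3 requires an abnormal TG or HDL-C. Section 1 gives the purpose as choosing, in each food matrix, the product with the greatest effect on TG or HDL-C.

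**The concern.** The working quantity of this trial is the precision of five arm means, each from 20 people. An analysis of change without the baseline as covariate in effect fixes the slope of the day-28 value on baseline at 1. When participants enter because a lipid value is abnormal, and lipids vary from visit to visit, the true slope is likely to be below 1, so change will depend on where a participant started. Some participants qualify through TG and others through HDL-C, so starting values will be spread out. Chance differences in baseline between arms of 20 then add noise to the differences in mean change. A covariate that is already collected would remove that noise.

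Sex is a smaller matter. The lists are stratified by it, but the named model does not reflect that.

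**Working it through.** **The plan's own figure.** Section 3.2 gives 20 per arm, and 3 × 5 × 20 = 300 agrees with section 3.1. No alpha, power, effect size, SD or correlation is given, so the 20 itself cannot be reproduced. With an assumed two-sided 5% level and 80% power, the detectable pairwise difference is (1.960 + 0.842) × √(2/20) = 0.886 SD of the change (normal approximation).

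**Effect of adding baseline.** Let σ² be the variance at each visit (assumed equal) and ρ the correlation between visits.

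- Change score: variance 2σ²(1 − ρ)
- Baseline-adjusted: residual variance σ²(1 − ρ²)
- Ratio, adjusted to change score: (1 + ρ)/2, a reduction of (1 − ρ)/2

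| assumed ρ | change, σ² units | adjusted, σ² units | variance reduction | SE reduction | adjusted n per arm equal to 20 unadjusted | power where the change score has 80% |
|---|---|---|---|---|---|---|
| 0.5 | 1.00 | 0.75 | 25% | 13.4% | 15 | 89.9% |
| 0.7 | 0.60 | 0.51 | 15% | 7.8% | 17 | 86.0% |
| 0.8 | 0.40 | 0.36 | 10% | 5.1% | 18 | 84.0% |
| 0.9 | 0.20 | 0.19 | 5% | 2.5% | 19 | 82.0% |

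These are large-sample formulas. If the variances differ between visits, the condition for a gain is that the regression slope differs from 1, and the size changes accordingly.

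**Change or day-28 value as response.** Write Y for day 28 and X for baseline. The model Y − X = arm + cX + error is the same as Y = arm + (c + 1)X + error. The arm contrasts and their standard errors are identical, so change can remain the response.

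**Effect of adding sex.** Each list holds 60 numbers per sex, so 60/5 = 12 per arm and sex. If sex explains a share R² of the residual variance, the SE falls by 1 − √(1 − R²): 0.5%, 2.5% and 5.1% at assumed R² of 1%, 5% and 10%. Differencing has already removed a constant difference in level between men and women, so the lower end is more likely.

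**Validity.** Lognormal TG was simulated with no treatment effect: 20 per arm, log-SD 0.3 to 0.5, ρ 0.5 to 0.85, 4,000 runs per setting. Type I error was between 4.2% and 5.7% for change scores and baseline-adjusted analyses alike, on the raw and on the log scale.

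**Scale of TG, as a side check.** With an assumed log-SD of 0.4 and a 20% multiplicative difference, power was:

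| ρ | raw change | raw, baseline-adjusted | log change | log, baseline-adjusted |
|---|---|---|---|---|
| 0.5 | 33% | 46% | 40% | 50% |
| 0.7 | 50% | 62% | 60% | 67% |
| 0.85 | 77% | 85% | 87% | 89% |

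Once baseline is in the model, the log scale adds about 4 to 5 points. Lognormal data with a multiplicative effect favour the log scale by construction.

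**The case against.** **Covariates belong in the SAP.** The word *including* in 6.4 does not close the list of effects, and an SAP that is not shown may add to it. This limits the point, and it would be wrong to say that the protocol excludes baseline or sex. But 6.4 is not silent: it sets the response, the model class and two effects, and it extends the same approach to the secondary variables. An analyst who followed it as written would fit a less efficient model than the collected data allow.

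**Change was chosen deliberately.** The laboratory SOPs (9.5 to 9.7) say that analysers cannot be harmonised and that the focus is therefore on change from day 0 to day 28. That reason survives adjustment. Each centre studies one matrix, so a constant analyser offset is absorbed by the matrix term, and change may stay as the response.

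**Stronger readings that the documents do not support.**

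- *A reader might infer bias.* Under randomisation the contrast of mean changes is unbiased, and its standard error already carries the baseline noise.
- *A reader might infer that TG is to be analysed untransformed.* No scale is stated, and silence is not a decision.
- *A reader might take the rule that "Triglyceride levels > 1000 mg/dL will be notified to the participant medical doctor" as a sign that extreme values will dominate.* It is a notification rule in a laboratory SOP and does not show who enrols. Section 3.4 excludes familial dyslipidaemia and lipid-active drug therapy. There is no explicit upper limit for TG, but domination by a few participants is not shown.
- *A reader might treat the unlisted stratum as a serious loss.* The likely gain in precision from sex is small.

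**The gain may be modest.** This stands. At ρ = 0.9 the standard error falls by only 2.5%.

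**Conclusion.** The point holds as one of efficiency. Section 6.4 names neither the own baseline value, which is complete in the full analysis set, nor the sex stratum of 6.1. The comparison it describes is valid but less precise than one adjusted for baseline. With equal variances at both visits, residual variance would fall by 25%, 15%, 10% and 5% at ρ of 0.5, 0.7, 0.8 and 0.9. At ρ = 0.5, 15 adjusted participants per arm do the work of 20 unadjusted ones.

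The algebra is firm. Its size rests on ρ, which the documents do not give. The case for sex rests on agreement between randomisation and analysis more than on precision. The power figures for TG rest on an assumed distribution and effect, and only illustrate the point.

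**What to change.** In section 6.4:

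- Add the corresponding baseline value and sex as covariates in the models for TG and HDL-C. The response may be change or the day-28 value.
- Do the same for each secondary variable, with its own baseline.
- Keep mean change with its 95% CI as a descriptive summary.

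An optional refinement, as no scale is stated, is to analyse log TG with log baseline. Results would then be ratios of geometric means instead of differences in mg/dL, so the choice should be written down before unblinding.

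The Visit 2 value should serve as the baseline on its own. Averaging it with the screening value is not advised, because screening values determine eligibility and are therefore selected.

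The cost is a change of wording and two degrees of freedom, one for baseline and one for sex. Within one matrix of 100 participants and five arms, the residual degrees of freedom go from 95 to 93. No new data, visits or participants are needed.
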